**Statistical analysis plan (SAP) for the (cost-)effectiveness of:
an innovative, personalised intervention of therapeutic Virtual
Reality (VR) IntEgrated within physioTherapY for a subgroup of
complex chronic low back pain (CLBP) patients (VARIETY-study)**

Publication date: 27-01-2023

Sponsor: ZonMw (10270032021502)

Document version: 1.0

Trial registration: ClinicalTrials.gov (ID: NCT05701891)

Main applicant:

[name], HAN

Principal investigator:

[name], HAN

Co-applicants:

[name], VU

[name] [name], Maastricht University

[name] [name], HAN

[name] [name], Radboudumc

[name] [name], Radboudumc

Study objectives and outcomes

Main objective

- To evaluate the effectiveness of physiotherapy with integrated multimodal VR for patients with complex CLBP, compared to usual primary physiotherapy care on physical functioning evaluated by the Oswestry Disability Index (ODI) at 3 months (primary end-point) and 12 months follow-up.

Secondary objective

- To evaluate the effectiveness of physiotherapy with integrated multimodal VR for patients with complex CLBP, compared to usual primary physiotherapy care on secondary outcome measures pain intensity, pain related fears, pain self-efficacy, physical activity level, global perceived effect and problems with activities at 3 months (primary end-point) and 12 months follow-up.
- To evaluate the cost-effectiveness of physiotherapy with integrated multimodal VR for patients with complex CLBP, compared to usual primary physiotherapy care for the 12-month period.

Trial methods

Design

- This study is a pragmatic, multicenter, two-arm, parallel, superiority, cluster-randomized controlled trial. Outcome variables will be measured at baseline, after 1 month (T1; during treatment), 3 months (T3; directly post-treatment), 6 months (T6; 3 months post-treatment) and 12 months (T12; 9 months post-treatment) follow-up, as described in table 1.

Randomization

- Eligible physiotherapists will be randomized on practice level using an online software program and stratified for completion of the three-year master to specialize as a psychosomatic physiotherapist.

Allocation

- Patients will be treated by their physiotherapist and follow the intervention their physiotherapist was randomized to.

Blinding

- Patients cannot be blinded, but will only be informed about their own intervention and will neither be informed about the presence of two arms in the trial nor the intervention received in the other arm.
- Blinding of participating physiotherapists is not possible, due to the nature of the intervention.
- Blinding of coordinating researchers is not possible, as they need information about treatment allocation for adequate study coordination.
- Blinding of the analyses will be achieved by an independent statistician blinded for treatment allocation, who will perform the primary study analyses.

Sample size

- A clinically relevant between-group difference of at least 10 points on the ODI after 3-months follow-up is expected, which seems plausible based on recent pilot studies with VR from our research group and others. For this expected and clinically relevant difference of 10 and a standard deviation of 15, 60 patients are needed per group ($\alpha=0.05$; power=90%; ICC for clusters 0.05; 15% drop-out). We expect to include 1 patient every 2 months per physiotherapist. A total of 20 participating physiotherapists will result in a total of 120 patients after 12 months.

Time schedule

- This study will start in the first quarter of 2023. Data collection will last until the first quarter of 2025.
- Approval from the medical-ethical committee (METC Oost-Nederland) was granted (case number: 2022-15794).
- The trial was registered with ClinicalTrials.gov (ID: NCT05701891).

Statistical principles

- All analyses in this plan are a priori analyses in that they have been defined in the protocol.
- All outcomes are analyzed for superiority of the experimental group in favor of the control group.
- All analyses described in the plan will take place after database locking, which will occur once all participants have finished their final measurement. An independent statistician that will be blinded for allocation will perform the main analyses.
- All statistical tests will be two-sided and the nominal p-value will be reported. All confidence intervals presented will be 95% and two-sided. The assumption of normal distribution will be checked by visual inspection of Q-Q plots. For skewed data, the interquartile range will be reported.
- Statistical significance is claimed if the null hypothesis is rejected at the significance level (alpha) of $p \leq 0.05$ (one-sided).
- Continuous variables will be summarized by means and SDs in case of a normal distribution and by median and interquartile range in case of a skewed distribution.
- Categorical variables will be summarized by frequencies and percentages.

Hypotheses

- This study is designed to assess the superiority of physiotherapy with integrated multimodal VR for patients with complex CLBP, compared to usual primary physiotherapy care on physical functioning at 3 months (primary end-point) and 12 months follow-up.
- The null hypothesis is that participants in the experimental group report a similar physical functioning score at 3 months and 12 months follow-up, as participants in the control group.
- The alternative hypothesis is that participants in the experimental group report a significantly higher score on physical functioning at 3 months and 12 months follow-up, as participants in the control group.

Analysis population

We will use the following definitions of analysis populations:

- The intention-to-treat population is defined as all participants provided informed consent and randomized to treatment.
- The per-protocol population is defined as all participants without minor and major protocol deviations.

We will decide which analysis populations each patient belong to in advance of database locking.

Protocol deviations

Major deviations

- For both treatment arms:
 - A total of <4 physiotherapy sessions or >30 physiotherapy sessions during intervention period (recommended: 8 – 25 sessions).
 - None of treatment modalities during the intervention period were exercise therapy or pain education.
 - Patient received invasive treatment (e.g. operation, injection or nerve block) for CLBP during intervention period.
- Specifically for experimental arm:
 - <300 minutes of VR use (50% of minimal dosage) during intervention period.

Minor deviations

- Specifically for experimental arm:
 - <480 minutes of VR use (80% of minimal dosage) during intervention period.

Trial population

- The following figures will be presented in a flow diagram, based on the CONSORT recommendations (figure 1):
 - Number of potentially eligible participants screened by the physiotherapist

- Number of included participants
- Reasons for non-inclusion
- Reasons for loss to follow-up and withdrawal
- Final inclusions in intention-to-treat analysis

Baseline patient and physiotherapist characteristics

- Participating patients will be described using the following baseline characteristics: age, sex, BMI, tobacco use, duration of complaints, comorbidities, occupation, education level, diagnostic and therapeutic procedures in past 6 months, medication use and experience with VR for treatment and entertainment, as shown in table 2. Moreover, participants will be described using the following clinical outcome measures: physical functioning, pain intensity, pain related fears, pain self-efficacy, physical activity level, problems with activities and intervention expectations.
- Participating physiotherapists will be described using the following baseline characteristics: age, gender, number of years' experience as a physiotherapist and specialization (i.e. finished with a master's degree), as shown in table 3.

Process evaluation

- The following process parameters regarding the physiotherapy treatment will be monitored by the physiotherapists for both arms: number of sessions, duration of sessions, applied treatment modality per session and adverse events (if applicable).
- In the experimental arm, the following VR related parameters will be additionally monitored using an online dashboard: treatment modality, daily treatment duration and VAS pain score (before and after VR use).

Analysis

Primary analysis

- The primary analysis will be an intention-to-treat, longitudinal mixed-model analysis comparing the effectiveness of physiotherapy with integrated multimodal VR for patients with complex CLBP, compared to usual primary physiotherapy care on physical functioning at 3 months (primary end-point) and 12 months follow-up.
- All participants in this study will be analyzed using mixed-models with maximum likelihood estimation.
- The analysis will be adjusted for important prognostic characteristics that potentially confound the treatment effects (e.g. physical functioning, pain severity, pain-related fears, BMI, tobacco use) and the baseline value of the outcome measure, with addition of other patient and/or physiotherapist characteristics that substantially differ between the two arms at baseline.

Secondary analysis

- Clinical effectiveness on secondary outcome measures:
 - The secondary effectiveness analysis will be performed similarly as the primary effectiveness analysis: an intention-to-treat, mixed-model analysis, to evaluate the effectiveness of physiotherapy with integrated multimodal VR for patients with complex CLBP, compared to usual primary physiotherapy care on pain intensity, pain related fears, pain self-efficacy and problems with activities at 3 months (primary end-point) and 12 months follow-up.

Cost-effectiveness

- Health-related Quality of Life: At baseline, 3, 6, and 12 months after start of the intervention, the participants' health states were assessed using the EuroQol 5D Health Questionnaire 3-level version (EQ-5D-5L). Using the Dutch EQ-5D-5L tariff, these health states were converted into utility values (0=dead; 1=full health). Quality-adjusted life-years (QALYs) were calculated using the area under the curve approach.
- Costs: In line with Dutch guidelines, costs were assessed from a societal perspective, meaning that all costs were included irrespective of who paid or benefited.

- Data on other healthcare utilization, informal care, unpaid productivity, and absenteeism. For the cost-utility and -effectiveness analyses, all participants included in the study will be analyzed, with missing data handled by using Multivariate Imputation by Chained Equations (MICE) and the number of imputed datasets will be determined using the loss of efficiency approach. Imputation models will include all available cost and effect measure values as well as variables differing between groups at baseline, variables related to the “missingness” of data and variables related to the outcomes. Pooled estimates will be calculated using Rubin’s rules.
- Costs and effect differences will be estimated using Seemingly Unrelated Regression analyses, in which their possible correlation can be accounted for. The 95% confidence intervals surrounding the cost differences will be estimated using Bias-Corrected and Accelerated (BCA) bootstrapping. Subsequently, Incremental Cost-Effectiveness Ratios (ICERs) will be calculated by dividing the differences in costs by the differences in QALYs. Uncertainty surrounding the cost-differences and ICERs will be estimated using bias correct and accelerated (BCA) bootstrapping techniques (5000 replications) and be graphically illustrated by plotting BCA-bootstrapped cost-effect pairs on cost-effectiveness planes. Also, cost-effectiveness acceptability curves will be constructed to provide an indication of the probability of physiotherapy with integrated multimodal VR therapy being cost-effective with usual care at different values of willingness to pay.

Responder analysis

- The proportion of participants with a minimal clinically important difference (MCID), responders, on each of the outcome variables between treatment arms, at 3 months and 12 months follow-up:
 - 8 points improvement on the ODI (Hung et al., 2018)
 - 15% and/or 1-point improvement on the NRS (Salaffi et al., 2004)

Availability of data and materials

- The datasets generated and analyzed during the current study will be available in the Dataverse repository.
- The research protocol is accessible at ClinicalTrials.gov (ID: NCT05701891).

Figure 1. *Flow of participants*

[figure not shown]

Table 1. *Overview of measurements*

	T0	T1	T3	T6	T12
Primary outcome measure					
Oswestry Disability Index (ODI)	X	X	X		X
Secondary outcome measure					
Numeric Rating Scale (NRS)	X	X	X		X
Fear Avoidance Beliefs Questionnaire (FABQ)	X	X	X		X
Pain Catastrophizing Scale (PCS)	X	X	X		X
Physical activity (self-reported)	X	X	X		X
Global perceived effect (GPE)		X	X		X
Patient-specific complaints questionnaire (PSK)	X		X		X
Pain self-efficacy (PSEQ)	X	X	X		X
Credibility and expectancy questionnaire (CEQ)	X	X			
Igroup presence questionnaire (IPQ)		X	X		
Economic parameters					
Quality-adjusted life years (QALY) (EQ-5D-5L)	X		X	X	X
Health-related and work-related costs	X		X	X	X
Patient characteristics	X				
Treatment parameters					
Other treatment than PT because of LBP, in past 12 weeks			X		
Duration of PT-treatment (number of weeks/sessions, reported by PT)			X		
Content of PT-treatment (usage of treatment modalities, reported by PT)			X		

Table 2. *Baseline characteristics*

	Experimental group (n =)	Control group (n =)
General characteristic		
Age (years), mean \pm SD		
Sex (female (n)), %		
BMI, mean \pm SD		
Smoker (yes), %		
Duration of symptoms (years), mean \pm SD		
Work status		
Paid work (fulltime), %		
Pain work (parttime), %		
Unpaid work, %		
No work, but not retired, %		
Retired, %		
Student, %		
Use of pain medication (yes), %		
Comorbidities affecting daily life (count), %		
Diagnostic procedures for CLBP in past 6 months (yes), %		
Treatment for CLBP in past 6 months (yes), %		
Experience with VR for treatment (yes), %		
Experience with VR for entertainment (yes), %		

Table 3. *Physiotherapist characteristics*

	Experimental group (n =)	Control group (n =)
General characteristic		
Age (years), mean \pm SD		
Sex (female), %		
Years' experience as physiotherapist (years), mean \pm SD		
Specialization		
Manual, %		
Sport, %		
Psychosomatic, %		
Children, %		
Geriatric, %		
Orofacial, %		
Pelvic, %		
Oncology, %		

Table 4. *Primary and secondary outcome measures*

	Exp. (n=)	Control (n=)	Est. diff. between groups	
			Crude (95% CI, p-value)	Adj. (95% CI, p-value)
Primary clinical outcomes				
Physical function (ODI), mean \pm SD				
Baseline				
1 months follow-up				
3 months follow-up				
12 months follow-up				
Secondary clinical outcomes				
Pain intensity (NRS), mean \pm SD				
Baseline				
1 months follow-up				
3 months follow-up				
12 months follow-up				
Pain related fears (FABQ), mean \pm SD				
Baseline				
1 months follow-up				
3 months follow-up				
12 months follow-up				
Pain related fears (PCS), mean \pm SD				
Baseline				
1 months follow-up				
3 months follow-up				
12 months follow-up				
Physical activity, mean \pm SD				
Baseline				
1 months follow-up				
3 months follow-up				
12 months follow-up				
Global perceived effect (at least 'much improved'), %				
3 months follow-up				

	Exp. (n=)	Control (n=)	Est. diff. between groups	
12 months follow-up				
Activity level (PSK)				
Baseline				
3 months follow-up				
Pain self-efficacy (PSEQ), mean \pm SD				
Baseline				
1 months follow-up				
3 months follow-up				
12 months follow-up				
Treatment expectation (CEQ), mean \pm SD				
Baseline				
1 months follow-up				
Sense of presence (IPQ), mean \pm SD				
1 months follow-up				
3 months follow-up				

Table 5: Costs per arm and cost differences across arms

Costs during 12-month follow-up period*	Experimental group (n=), mean costs in € (SE)	Control group (n=), mean costs in € (SE)	Crude mean cost difference in € (SE)	Adjusted* mean cost difference in € (SE)
Intervention-related costs				
Primary health care costs (other than intervention) ^a				
Secondary health care costs ^b				
Medication costs ^c				
Presenteeism costs				
Absenteeism costs				
Unpaid productivity costs				
Informal care costs				
Total costs				

SE = standard error, CI = confidence interval.

*adjusted for treatment arm, baseline costs, QALY, work status, gender, age

- a. primary health care, other than the (experimental or control) intervention (e.g., general practitioner, acupuncturist);
- b. secondary health care (e.g., hospital, rehabilitation center);
- c. (prescribed and over-the-counter) medication for low back pain.

Table 6. *Cost-effectiveness analysis*

Analysis	Sample size		Outcome	ΔC (95 % CI)	ΔE (95 % CI)	ICER	Distribution CE-plane (%)			
	EXP	CON		€	Points		€/point	NE ^a	SE ^b	SW ^c
Main analysis— imputed dataset			ODI (0-100)							
			NRS pain (0-10)							
			QALYs (range: 0–1)							
SA1—health care perspective			ODI (0-100)							
			NRS pain (0-10)							
			QALYs (range: 0–1)							
SA2—human capital approach			ODI (0-100)							
			NRS pain (0-10)							
			QALYs (range: 0–1)							
SA3—complete cases for cost outcomes only			ODI (0-100)							
			NRS pain (0-10)							

Analysis	Sample size		Outcome	ΔC (95 % CI)	ΔE (95 % CI)	ICER	Distribution CE-plane (%)			
	EXP	CON		€	Points	€/point	NE ^a	SE ^b	SW ^c	NW ^d
			QALYs (range: 0–1)							
SA4-a – per protocol cases only (excluding major protocol violators only)			ODI (0-100)							
			NRS pain (0-10)							
			QALYs (range: 0–1)							
SA4-b– per protocol cases only (excluding major and minor protocol violators)			ODI (0-100)							
			NRS pain (0-10)							
			QALYs (range: 0–1)

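### The planned 60 patients per group give about 85% power, not 90%, under the SAP's two-sided rule; 60 is enough only under its conflicting one-sided sentence, with physiotherapist-sized clusters.

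*SAP*

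**What the plan says.** The Sample size section of the SAP expects a between-group difference of 10 ODI points at 3 months and concludes: "For this expected and clinically relevant difference of 10 and a standard deviation of 15, 60 patients are needed per group". The accompanying parenthesis sets alpha at 0.05, with no sidedness, and lists "power=90%; ICC for clusters 0.05; 15% drop-out". On recruitment it says "A total of 20 participating physiotherapists will result in a total of 120 patients after 12 months", at a rate of one patient per physiotherapist every two months.

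The Statistical principles section gives two rules on sidedness. One is "All statistical tests will be two-sided and the nominal p-value will be reported", accompanied by a commitment to two-sided 95% confidence intervals. The other is "Statistical significance is claimed if the null hypothesis is rejected at the significance level (alpha) of $p \leq 0.05$ (one-sided").

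On the unit of allocation, the Randomization section says "Eligible physiotherapists will be randomized on practice level using an online software program". The SAP gives neither the number of practices nor the number of patients per practice.

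**The concern.** The SAP states all the inputs to its sample size except the sidedness of alpha and the cluster size. The cluster size per physiotherapist can be derived from its own recruitment figures. The sidedness cannot be settled, because the document states both versions, and the choice decides whether 60 per group delivers the claimed 90%.

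The two-sided calculation also reaches exactly 60 before any allowance for drop-out. That raises the question whether the listed 15% was ever applied. The document does not show which route was taken.

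There is a further difficulty with the cluster. The derivable size is per physiotherapist, but the practice is what is randomised. If some practices contribute more than one physiotherapist, the clusters are larger and fewer, and the design effect rises.

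What is at stake is how the trial is read. If the two-sided rule governs, a null primary result would be judged against a planned power about 5 percentage points too high. The planned type II error would be about 15% instead of 10%.

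**Working it through.** **Inputs from the SAP (Sample size section).** Difference 10; SD 15; alpha 0.05; power 90%; ICC 0.05; drop-out 15%; 120 patients and 20 physiotherapists.

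**Derived.** Patients per physiotherapist: 120/20 = 6. The accrual rate agrees: 12 months at one per two months is 6, and 20 × 6 = 120. After 15% drop-out there are 60 × 0.85 = 51 evaluable per group and 6 × 0.85 = 5.1 completers per physiotherapist.

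**Formulas (normal approximation, unadjusted comparison).**
- Per-group size without clustering: n0 = 2 (z_alpha + z_power)² (SD/difference)²
- Design effect: DE = 1 + (m − 1) × ICC
- Enrolled per group: n0 × DE / 0.85
- Power: Φ(δ − z_alpha), where δ = 10 / (15 √(2 DE / 51))

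**Two-sided 0.05**
- n0 = 2 (1.960 + 1.2816)² (1.5)² = 47.28, rounded up to 48.
- DE at m = 6 is 1 + 5 × 0.05 = 1.25.
- 48 × 1.25 = 60. This matches the SAP's figure, but before drop-out.
- With drop-out: 47.28 × 1.25 / 0.85 = 69.5. With m = 5.1, DE = 1.205 and the requirement is 47.28 × 1.205 / 0.85 = 67.0.
- Power with 51 evaluable: δ = 3.011 and Φ(3.011 − 1.960) = 85.3% at m = 6; δ = 3.067 and 86.6% at m = 5.1.

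**One-sided 0.05**
- n0 = 2 (1.645 + 1.2816)² (1.5)² = 38.54.
- 38.54 × 1.25 / 0.85 = 56.7. Rounding up at each step gives 58; starting from a t-based 40 per group gives 59. So 60 is enough.
- Power with 51 evaluable: Φ(3.011 − 1.645) = 91.4% at m = 6, and 92.2% at m = 5.1.

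**Practice as the cluster.** The SAP does not give the number of practices. The table assumes two physiotherapists per practice, hence 10 practices. The ICC of 0.03 is a second assumption, included because a practice-level ICC may be smaller. Each range runs from clusters counted as enrolled (m = 6 or 12) to clusters counted as completers (m = 5.1 or 10.2).

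| Cluster | ICC | Two-sided power | One-sided power |
|---|---|---|---|
| Physiotherapist, m = 6 to 5.1 | 0.05 (stated) | 85.3% to 86.6% | 91.4% to 92.2% |
| Practice, m = 12 to 10.2 (assumed) | 0.05 (stated) | 77.2% to 79.6% | 85.5% to 87.3% |
| Practice, m = 12 to 10.2 (assumed) | 0.03 (assumed) | 83.1% to 84.6% | 89.9% to 90.9% |

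**Baseline adjustment.** Take SD 15 as an unadjusted SD and let adjustment multiply the variance by 1 − r², with the ICC unchanged (both assumptions). Two-sided 90% with 51 evaluable per group then requires 47.28 × DE × (1 − r²) = 51. This gives r = 0.37 (m = 6) or 0.32 (m = 5.1) with physiotherapist clusters, and r = 0.55 (m = 12) or 0.51 (m = 10.2) with 10 practices at ICC 0.05.

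**Small number of clusters.** Replacing the normal approximation by a t distribution with 18 degrees of freedom (20 clusters less 2) lowers the two-sided figure for physiotherapist clusters to about 81% to 83%.

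**The case against.** The strongest reply is that 60 is not an arithmetic error. With every listed input, and under the SAP's own one-sided significance sentence, 57 to 59 per group are enough. That is correct. The defect is that the claimed power depends on which of two contradictory rules applies.

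Second, the Primary analysis section adjusts for prognostic variables "and the baseline value of the outcome measure, with addition of other patient and/or physiotherapist characteristics". If SD 15 is unadjusted, a baseline correlation of 0.4 gives 90.7% two-sided power and 0.5 gives 93.5% (m = 6, correlations assumed). This stands as a possibility. However, the sample-size statement claims no such gain, gives no correlation, and does not say whether SD 15 is before or after adjustment. The 85% is therefore the power on the stated inputs, not necessarily that of the final model.

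Third, the 15% drop-out may refer to the whole 12 months. If loss by 3 months were 5% to 10% (assumption), unadjusted two-sided power would be about 87% to 89%. Patients with a 1-month ODI but no 3-month value also contribute to a likelihood-based mixed model. Still, the statement concerns the 3-month difference, and applying its drop-out there is the natural reading.

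Fourth, the practice scenarios rest on assumed numbers. They do, and they serve only to show direction and size. The conclusion for physiotherapist clusters does not need them. At the stated ICC, one-sided 90% survives up to about 1.25 physiotherapists per practice.

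Finally, enrolment and analysis are unaffected, and a null result should be read against its confidence interval. That limits the harm but does not make the stated power correct.

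**Conclusion.** The concern holds. On the SAP's stated inputs with 6 patients per physiotherapist, 60 enrolled per group give 85.3% to 86.6% power at two-sided 0.05, and 67 to 70 per group would be needed for 90%. At one-sided 0.05 the same 60 give 91.4% to 92.2%. Since the SAP states both rules, its 90% cannot be relied on as written.

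These figures assume an unadjusted comparison, the normal approximation and all of the 15% drop-out falling by 3 months. Effective baseline adjustment or less early drop-out would raise them; a small-sample correction for 20 clusters would lower them. At the stated ICC, even the one-sided support for 60 requires about one physiotherapist per practice. The SAP does not say whether that is so.

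**What to change.** Keep 120 patients and change the text as follows.

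1. Reconcile the two sidedness sentences in Statistical principles, and put the sidedness next to alpha in the Sample size section. Two-sided is the version consistent with the two-sided 95% confidence intervals already planned. If one-sided is kept, label it as such.
2. State the expected number of practices and patients per practice, and recompute the power with the practice as the cluster, showing the design-effect and drop-out steps.
3. Report the resulting power. If practices contribute one physiotherapist each and two-sided testing is kept, the sentence could read: *With 60 enrolled per group, 15% drop-out, ICC 0.05 and 6 patients per cluster, power for an unadjusted comparison is about 85% at two-sided alpha 0.05.* Under one-sided testing the corresponding figure is about 91%. If practices are larger, use the recomputed figure instead.
4. If baseline adjustment is relied on to reach 90% two-sided, state the assumed correlation between baseline and 3-month ODI: about 0.32 to 0.37 with physiotherapist clusters, or 0.51 to 0.55 with 10 practices at ICC 0.05.

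The cost is SAP wording and one recalculation. No extra patients are needed and the analysis model does not change. If the two-sided rule is kept, the stated power becomes less favourable.

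### The SAP makes every test and 95% CI two-sided, then claims significance at one-sided p ≤ 0.05, and nothing says which rule decides the primary analysis

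*SAP*

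**What the plan says.** Two adjacent bullets under Statistical principles set the inferential rules. The first says "All statistical tests will be two-sided and the nominal p-value will be reported" and adds "All confidence intervals presented will be 95% and two-sided". The second says "Statistical significance is claimed if the null hypothesis is rejected at the significance level (alpha) of $p \leq 0.05$ (one-sided").

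The other places where the rule could be settled do not settle it:

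- **Sample size** gives alpha without a side: "60 patients are needed per group ($\alpha=0.05$; power=90%; ICC for clusters 0.05; 15% drop-out").
- **Hypotheses** pairs a null of similar scores with a directional alternative, that "participants in the experimental group report a significantly higher score on physical functioning at 3 months and 12 months follow-up".
- **Primary analysis** specifies an intention-to-treat longitudinal mixed model and mentions neither alpha nor sidedness.
- **Table 4** has columns that show a 95% CI and a p-value together for each between-group difference.

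**The concern.** A test cannot be two-sided and also be judged at one-sided 0.05. At the same nominal level the two rules use different critical values, and the one-sided rule corresponds to a 90% two-sided interval, not the 95% interval that the SAP requires. If the second bullet is followed, the trial can be declared positive on 3-month ODI while the CI in the same row of Table 4 includes zero. If the first is followed, the sample-size statement may not deliver its 90% power. With both rules in the plan, the choice could be made after the results are known. Because the bullets cover all tests, the 12-month and secondary outcomes are affected too.

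**Working it through.** **Inputs from the SAP (Sample size):** difference 10 ODI points, SD 15, α = 0.05, power 90%, ICC 0.05, drop-out 15%, 60 per group, 20 physiotherapists for 120 patients.

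**Assumed cluster size.** The SAP gives none. 120/20 = 6 patients per physiotherapist, or 6 × 0.85 = 5.1 after drop-out. I treat the physiotherapist as the cluster and use 5.1 to 6.

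**1. Which sidedness reproduces 60 per group?** Per-group n = 2 × (15/10)² × (z_α + 1.282)², multiplied by the design effect 1 + (6 − 1) × 0.05 = 1.25 and divided by 0.85.

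| Rule | Basic n | × 1.25 | ÷ 0.85 |
|---|---|---|---|
| One-sided (1.645) | 38.5 | 48.2 | 57 (58 if the basic n is first rounded up to 39) |
| Two-sided (1.960) | 47.3 | 59.1 (60 if the basic n is first rounded up to 48) | 70 (71 if rounded up first) |

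With every stated input, 60 is close to the one-sided figure. But 48 × 1.25 = 60 exactly is the two-sided figure before drop-out. The number therefore cannot show which rule was meant.

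**2. Thresholds.** Completers per arm: 60 × 0.85 = 51. SE = 15 × √(2 × DE/51), normal approximation, no covariate adjustment.

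| Cluster size | DE | SE | One-sided threshold (1.645 × SE) | Two-sided threshold (1.960 × SE) |
|---|---|---|---|---|
| 5.1 | 1.205 | 3.26 | 5.36 | 6.39 |
| 6 | 1.25 | 3.32 | 5.46 | 6.51 |

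An estimate between the two thresholds is significant under one bullet and not under the other, and its 95% CI includes zero.

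**3. How often that happens.** The probability is Φ((upper threshold − δ)/SE) − Φ((lower threshold − δ)/SE). For a true difference δ of 0 it is 2.5%, which is the gap between false-positive rates of 5% and 2.5%. For δ = 5 it is about 12%, and for δ = 10 about 6%.

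**4. Power for 10 points with 60 per group.** Power = Φ(10/SE − z).

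| Cluster size | One-sided | Two-sided |
|---|---|---|
| 5.1 | 92.2% | 86.6% |
| 6 | 91.4% | 85.3% |

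**5. Sensitivity to larger clusters.** The SAP says "Eligible physiotherapists will be randomized on practice level using an online software program" and does not give the number of practices. If each practice had two participating physiotherapists (an assumption), clusters would hold 10.2 to 12 patients. DE would be 1.46 to 1.55, SE 3.59 to 3.70, and two-sided power 80% to 77%. One-sided power would also fall below 90%, to about 87% to 86%.

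**The case against.** The contradiction itself is hard to dispute. The case on the other side concerns what follows from it.

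- **The SAP may lean one-sided.** Only one bullet says when significance is claimed. The alternative is directional, and 60 per group fits the one-sided calculation best. This is a fair reading, but a directional aim is also compatible with two-sided testing, and the SAP says all tests and all intervals are two-sided. The text does not decide.
- **The power shortfall may have another cause.** Sixty is exactly the two-sided requirement before drop-out, so the gap could be an omitted drop-out inflation. That stands, and it is why the power figures here illustrate the consequence and do not prove intent.
- **The 85–87% figure is not robust.** The primary analysis adjusts for baseline ODI. If SD 15 is unadjusted (the SAP does not say), a baseline–outcome correlation of about 0.32 to 0.37 restores 90% two-sided power, and 0.5 gives about 94%. In the other direction, a t reference with 18 degrees of freedom for 20 clusters gives about 81–83% two-sided. This stands too, so any restated power must carry its assumptions.
- **The harm is bounded.** Nominal p-values and 95% CIs will be reported, so readers could see a borderline result. That makes the conflict visible, but it does not say which conclusion the trial is entitled to draw.

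None of these points removes the conflict between the two bullets, which depends on no assumption about clusters, covariates or drop-out.

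**Conclusion.** The SAP is wrong as written and must be corrected before the analysis. It holds two incompatible rules for claiming significance, with critical values 1.645 and 1.960. They differ by about 1 ODI point in the threshold on the SAP's inputs and an assumed 5.1 to 6 patients per cluster. The stated 90% power is met under the one-sided rule and missed under the two-sided rule on that same unadjusted basis. The contradiction is certain; the power figures depend on the cluster size, which the SAP does not give, and on ignoring baseline adjustment.

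The intended direction is not in doubt. The superiority aim and the responder criterion of "8 points improvement on the ODI" both point to benefit from VR. Two other phrases therefore need only a wording correction: the higher score in the alternative hypothesis (a higher ODI means more disability), and "All outcomes are analyzed for superiority of the experimental group in favor of the control group".

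**What to change.** 1. **Statistical principles:** delete the one-sided qualifier, so that the significance rule matches the two-sided tests and 95% CIs already specified. This carries the same rule to the 12-month and secondary outcomes. Add for the primary endpoint: *Superiority is claimed if the two-sided p-value for the between-arm difference in ODI at 3 months is ≤ 0.05 and the difference favours the experimental arm.*
2. **Sample size:** state that α = 0.05 is two-sided, give the assumed cluster size, and restate the power for 60 per group with its assumptions. On the SAP's inputs, unadjusted, that is about 85–87% with 5.1 to 6 patients per cluster. If the sponsor counts on baseline adjustment or uses practices as clusters, the correlation or cluster size assumed should be shown.
3. **Wording only:** express the alternative hypothesis as a lower ODI (less disability) in the experimental arm, and say superiority *over* the control group.

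The cost is SAP text in three places, with no extra patients and no change of design. The sponsor accepts a threshold about 1 ODI point stricter than the one-sided rule and a stated power that may be below 90%, lower still if clusters are larger practices.
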